3.4 Study Endpoints

3.4.1 Primary Study Endpoint

The proportion of included patients with low synovitis scores will be calculated. Additionally, the proportion of patients with low-synovitis scores among those with disease activity score in 28 joints (DAS28 >3.2) will be evaluated. To assess patient characteristics associated with having low synovitis scores to inform inclusion criteria for a future interventional study, Fisher's exact tests will be used to compare the proportion of low synovitis scores in patients in certain prespecified subgroups:

- patients with long-standing versus earlier RA (>5 years vs ≤5 years)
- biologic vs. non-biologic treated patients, high versus low CRP (>1mg/dL vs. ≤1mg/dL)
- patients with vs. without evidence of central pain sensitization (PSD ≥12 vs <12)
- seropositive vs. seronegative
- patients with depression vs. those without (based on PROMIS vs. PHQ-9)
- moderate vs high disease activity by DAS28 and moderate vs high disease activity by CDAI
- associations with age, comorbidities, CDAI, DAS28, will also be assessed.

3.4.2 Secondary Study Endpoints

The frequency of changes in physician treatment recommendations after ultrasound will be calculated. Fisher's exact tests will be used to compare the proportion of patients for whom treatment escalation (dose increase or DMARD add/switch) is recommended before versus after ultrasound. Differences in disease activity assessment before and after ultrasound will also be compared with Fisher's exact tests, and differences in the provider's confidence in disease activity assessment (5-point Likert scale) before and after ultrasound will be compared with the nonparametric Wilcoxon Signed Rank test.

4. Study Population and Duration of Participation

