3.1 General Design

This single-arm pilot interventional study will evaluate the potential for ultrasound to improve disease activity assessments for patients with rheumatoid arthritis with clinical scores indicating moderate or high disease activity.

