3.2 Allocation to Interventional Group

All eligible and consented participants will receive a bilateral hand/wrist musculoskeletal ultrasound.

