5. C-reactive protein (CRP): Substance secreted by the liver. Routine blood test performed as part of standard clinical care to measure inflammation and assess disease activity in RA.
6. Musculoskeletal ultrasound (see below)

Chart review to obtain additional participant information:

- Demographics: Age, sex, race/ethnicity, BMI, smoking
- Medical History: RA disease duration, RF, CCP, current DMARDs, current glucocorticoid dose, current NSAID use, opioid use, number of previous biologics/JAKi
- Comorbidities: Presence of peripheral joint osteoarthritis, chronic back pain/back osteoarthritis, anxiety, depression, sleep apnea, fibromyalgia

Provider measures:

1. Pre-ultrasound assessment/treatment form:
 - Assessment of the patient's disease activity: providers will select whether they think the patient is in remission, low, moderate, or high disease activity (does not need to match the patient's CDAI score)
 - Confidence in the disease activity assessment (1-10) on a visual analog scale (VAS). A VAS tries to measure a characteristic or attitude that is believed to range across a continuum of values and cannot be easily directly measured.
 - Treatment recommendations: Providers will be asked whether their recommendation for treatment is as follows: no change, increase disease modifying anti-rheumatic drugs (DMARD) dose, or add/switch DMARD.
2. Post-ultrasound assessment/treatment form:
 - Same as the pre-ultrasound form but completed after ultrasound results are reviewed

Musculoskeletal ultrasound assessment

- Bilateral hands/wrists with gray-scale and power doppler (to be performed by the musculoskeletal ultrasound department or by an ultrasound certified rheumatologist within 3 weeks of visit 1. Synovitis in the metacarpophalangeal joint (MCPs), proximal interphalangeal joint (PIPs), and wrists will be graded as absent, mild, moderate, or severe according to the validated OMERACT scoring system. Images will be stored to allow a second reader to score images to assess inter-rater reliability.
 - OMERACT is the acronym for an international, informally organized network initiated in 1992 aimed at improving outcome measurement in rheumatology. Data driven recommendations are prepared and updated by expert working groups. Recommendations include core sets of measures for most of the major rheumatologic conditions
 - Patients in whom all measured joints have absent or mild synovitis will be considered to have low synovitis scores

CONFIDENTIAL

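### The before/after ultrasound comparisons of treatment escalation and disease-activity rating use Fisher's exact test, an independent-groups test, on data that are matched pairs

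*Combined protocol and SAP*

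**What the plan says.** Section 3.4.2 names Fisher's method for escalation: "exact tests will be used to compare the proportion of patients for whom treatment escalation (dose increase or DMARD add/switch) is recommended before versus" following the scan. For the second outcome it states: "Differences in disease activity assessment before and after ultrasound will also be compared with" the same method. The Aim 2 paragraph of Section 6.3.2 repeats both, and the Study Summary also names Fisher's test for these outcomes.

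The design gives one pair of ratings per patient. Section 3.1 describes a single arm. Section 3.2 says "All eligible and consented participants will receive a bilateral hand/wrist musculoskeletal ultrasound". In Section 3.3 the post-ultrasound provider form is described as "Same as the pre-ultrasound form but completed after ultrasound results are reviewed". On that form the treatment recommendation has three options ("no change, increase disease modifying anti-rheumatic drugs (DMARD) dose, or add/switch DMARD"), the last two of which are pooled as escalation. The disease-activity item has four ordered levels: "providers will select whether they think the patient is in remission, low, moderate, or high disease activity".

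For the remaining item on the form, the provider's confidence, Section 3.4.2 does choose a paired method: values "before and after ultrasound will be compared with the nonparametric Wilcoxon Signed Rank test". No section names a paired method for escalation or for the disease-activity rating.

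**The concern.** Fisher's exact test compares proportions between groups of different subjects. Here the before and after groups are the same patients, and a provider's second opinion will usually resemble the first. The test could be applied in two ways, and neither answers the question.

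- **Margins stacked as two groups.** Each patient is counted twice and the within-patient correlation is ignored. When that correlation is positive, the p-value is generally too large and a real shift can be missed.
- **Before cross-tabulated against after.** The test then measures whether the two ratings are associated. It is most significant when nobody changes their mind.

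The disease-activity rating has a further problem: Fisher's test ignores the order of its four levels.

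The secondary objective (Section 2.2) is to compare recommendations before and after ultrasound, and the Fisher test on escalation is the only inferential test named for it. Section 6.1 also says the pilot is to support power calculations for later studies. A paired follow-on design needs the discordant counts, which an analysis of the margins discards.

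**Working it through.** **Inputs.** Section 4.2 expects about 40 consented and 20 evaluable subjects, so both 20 and 40 pairs are used. The documents give no alpha, effect size or discordance rate, so there is no planned figure to reproduce. Two-sided 0.05 and all escalation and switching rates below are assumptions.

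**Notation.** Among n patients, a are escalated both times, b before only (switch down), c after only (switch up) and d neither time. The change in proportion is (b − c)/n. Fisher on the margins sees only a + b and a + c. Exact McNemar uses the discordant pairs:

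p = min{1, 2 × Σ C(b + c, k) / 2^(b + c)}, summed over k = 0 to min(b, c).

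**Step 1: example tables.**

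| Pairs | Escalated before → after | Down / up | Fisher p | Exact McNemar p |
|---|---|---|---|---|
| 20 | 14 → 8 | 6 / 0 | 0.111 | 2 × 1/64 = 0.031 |
| 20 | 14 → 8 | 7 / 1 | 0.111 | 2 × (1 + 8)/256 = 0.070 |
| 40 | 28 → 20 | 8 / 0 | 0.110 | 2 × 1/256 = 0.008 |
| 40 | 28 → 20 | 10 / 2 | 0.110 | 2 × (1 + 12 + 66)/4096 = 0.039 |

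Fisher's p-value does not move with the pairing, although the pairing carries the evidence about change.

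**Step 2: why.** The estimated variance of the paired difference is [(b + c)/n − ((b − c)/n)²]/n. For 28 → 20 of 40 with 8 down and 0 up, this is (0.20 − 0.04)/40 = 0.0040, a standard error of 0.063. Treating the margins as independent gives (0.70 × 0.30 + 0.50 × 0.50)/40 = 0.0115, a standard error of 0.107. With 10 down and 2 up, the paired value is (0.30 − 0.04)/40 = 0.0065, a standard error of 0.081.

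**Step 3: rejection rates.** These come from exact enumeration: sum n!/(a! b! c! d!) × p11^a × p10^b × p01^c × p00^d over all tables with p ≤ 0.05.

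*No true change (50% escalated both times):*

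| Pairs | Discordant | Fisher | McNemar |
|---|---|---|---|
| 20 | 20% | 0.0006 | 0.005 |
| 40 | 20% | 0.0009 | 0.019 |
| 40 | 30% | 0.006 | 0.024 |
| 40 | 50% (ratings independent) | 0.033 | 0.030 |
| 40 | 80% (ratings negatively correlated) | 0.093 | 0.031 |

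*True change, 70% escalated before:*

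| Pairs | Of those escalated, switch down | Of the rest, switch up | Fisher | McNemar |
|---|---|---|---|---|
| 20 | 30% | 5% | 6% | 19% |
| 20 | 20% | 5% | 1% | 4% |
| 40 | 30% | 5% | 27% | 71% |
| 40 | 30% | 15% | 17% | 44% |
| 40 | 30% | 30% | 9% | 19% |
| 40 | 20% | 5% | 4% | 34% |

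*True change, 60% to 40%:* at 40 pairs, power is 27% vs 84% with 20% discordant and 32% vs 57% with 30% discordant. At 20 pairs it is 5% vs 20% and 8% vs 20%. If the two ratings were independent, Fisher would lose nothing (37% vs 34% at 40 pairs).

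**Step 4: the cross-table reading.** If 24 of 40 are escalated both times and nobody changes, Fisher gives p = 1/C(40, 16) = 1.6 × 10⁻¹¹. With 15 both, 5 down, 5 up and 15 neither, Fisher gives p = 0.004, while McNemar gives p = 1.00 because net change is zero.

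**The case against.** The strongest reply concerns weight. Section 6.2 calls the analysis descriptive, Section 6.1 bases the sample size on feasibility and cost, and no decision rule depends on these p-values. The frequency of changed recommendations (Sections 3.4.2 and 6.3.2) and the tabulation of changed decisions (Section 6) do not depend on the test. With positively correlated ratings, the likelier error is a missed signal, not a false claim. All of this stands and limits the consequences. It does not make the named test valid: the plan commits to it in three places, and Section 12 plans a manuscript.

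The size of the effect is also open to challenge. Examples with no upward switches are the most favourable to McNemar. With one upward switch at 20 pairs, neither test reaches 0.05, and McNemar's power at 20 pairs is at most 20% in the scenarios above. This stands too: the correction restores validity but does not make 20 pairs informative.

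The cross-table reading fits the wording less well, since the text speaks of comparing proportions. It is the less likely use, though the plan does not say which table is meant.

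Finally, that the same provider completes both forms is inferred from Sections 3.3 and 5.2. Pairing by patient holds either way.

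**Conclusion.** The concern holds. Both before/after comparisons are specified with a test whose independence assumption the design violates, and no section supplies a paired alternative. On the likelier reading (margins), and with positive within-patient correlation, Fisher is too conservative: its type I error is 0.0009 to 0.006 at 40 pairs with 20–30% discordance, against a nominal 0.05. In the 40-pair scenarios with positively correlated ratings, its power runs from about one ninth to just over half that of exact McNemar (4% vs 34%; 32% vs 57%). It would be anti-conservative only if before and after ratings were negatively correlated. On the cross-table reading, the p-value does not address change at all.

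These sizes rest on assumed escalation and switching rates and an assumed two-sided 0.05; the direction rests only on positive correlation between the two ratings. The primary proportion and the Aim 1 subgroup tests, which compare different patients, are unaffected.

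**What to change.** Amend the Study Summary, Section 3.4.2 and Section 6.3.2 (Aim 2) together:

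- **Escalation (yes/no):** use the exact McNemar test. Report the paired difference in proportions with a 95% confidence interval and both discordant counts (escalate to not, and not to escalate).
- **Four-level disease-activity rating:** use the Wilcoxon signed-rank test, as already planned for confidence. A marginal-homogeneity test would be an acceptable alternative.
- **Aim 1 subgroups:** keep Fisher's exact test.

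A useful addition, separate from the correction, is to tabulate the discordant pairs by ultrasound result (low versus not low synovitis), so that shifts in opposite directions do not cancel. McNemar's test does not allow for several patients rated by one provider; the plan should state that limitation.

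The cost is wording only. No new data are needed, and the methods are available in Stata, the software named in Section 6.2.

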5.5 Safety Evaluation

All efforts to uphold patient safety will be obtained. Data and privacy protection will be ensured by administering surveys through Penn REDCap. Verbal and written consent will be obtained from potentially eligible or eligible participants before commencement of any study procedures. Staff performing the study ultrasound will have been properly trained. Although the potential for a confidentiality breach does exist, the research team will follow all standard procedures for training, consent, storage, and reporting to minimize potential exposure of patient information.

6. Statistical Plan

CONFIDENTIAL

The number of patients with evidence of synovitis on ultrasound will be tabulated and compared across key measures such as CDAI, depression scores, polysymptomatic distress questionnaire, and PROMIS pain. The analysis will also summarize and tabulate the number of patients for which the ultrasound information changed the decision-making of the clinical provider.

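### Aim 2 tests only the pooled before/after escalation proportion, and no planned summary shows whether changed recommendations follow the scan result

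*Combined protocol and SAP*

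**What the plan says.** Sections 3.4.2 and 6.3.2 (Aim 2) plan two things for treatment recommendations. The first is a count: "The frequency of changes in physician treatment recommendations after ultrasound will be calculated". The second is a Fisher's exact test to "compare the proportion of patients for whom treatment escalation (dose increase or DMARD add/switch) is recommended before versus after ultrasound". Provider ratings of disease activity are also to be compared before and after with Fisher's exact tests, again over all patients together.

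Section 6 adds a third summary: "The analysis will also summarize and tabulate the number of patients for which the ultrasound information changed the decision-making of the clinical provider".

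The design has one arm, and section 3.2 states: "All eligible and consented participants will receive a bilateral hand/wrist musculoskeletal ultrasound". Section 3.3 describes the second provider form as "Same as the pre-ultrasound form but completed after ultrasound results are reviewed", and places the scan "within 3 weeks of visit 1". Section 3.3 also defines low synovitis status for each scanned patient (no measured joint graded above mild). That status is the Aim 1 outcome; no Aim 2 analysis uses it.

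**The concern.** A scan can move a recommendation either way: down when little synovitis is seen, up when more is seen than expected. The pooled comparison sees only the net of the two. The change count sees the total, but not which way the changes went or whether they agreed with the image.

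There is also no second assessment made without the scan result. A provider who answers the same form again may answer differently for reasons unrelated to the ultrasound. The documents fix no date for either form. They also do not say whether the second form concerns the decision at visit 1 or the situation when the result arrives. Change of this kind enters both the count and the pooled comparison.

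The study is meant to supply planning data for a larger proposal. The rationale in section 1.1 is that falsely raised scores lead to unnecessary escalation. The useful quantity is therefore how often an escalation recommendation is dropped when synovitis is low, compared with when it is not. No planned summary gives that.

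**Working it through.** The plan states no effect size, alpha or power for Aim 2, so there is no figure to reproduce. The checks below are illustrations.

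**Inputs from the documents.** Section 4.2 expects about 40 consented to yield 20 evaluable; the Study Summary gives 40 subjects. Both sizes are used.

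**Assumptions.** The documents give no values for these: half the patients have low synovitis except where stated; escalation before ultrasound is 50% in steps 1 and 2, 60% in step 4, and 30% vs 70% in step 5; spontaneous flip rates are 5% to 20%; tests are two-sided at 0.05.

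**1. Cancellation.** Take 40 patients, 20 with low synovitis and 20 not, with 10 escalated in each group before the scan. Let 8 in each group change in the direction of the scan.
- Low synovitis: 10/20 escalated before, 10 − 8 = 2/20 after.
- Not low: 10/20 before, 10 + 8 = 18/20 after.
- Pooled: 20/40 before, 2 + 18 = 20/40 after. Fisher p=1.00.
- Exact McNemar, 8 vs 8 discordant pairs: p=1.00. A paired test alone does not cure the cancellation.
- Planned change count: 16/40 = 40% (95% CI 25% to 57%). It does not cancel, but it gives no direction.

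The opposing flows need not be exactly equal. With 6 down and 5 up among 20 patients, 11/20 = 55% changed, the net shift is 1/20 = 5 points, and exact McNemar gives p=1.0.

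**2. What the split shows in the same example.** Conditional on the pre-ultrasound recommendation, with Clopper-Pearson 95% intervals:

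| Escalations dropped | Low synovitis | Not low |
|---|---|---|
| 40 patients | 8/10 (44% to 97%) | 0/10 (0% to 31%) |
| 20 patients, same pattern | 4/5 (28% to 99%) | 0/5 (0% to 52%) |

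With all patients in each group as denominator, downward change is 8/20 vs 0/20 (Fisher p=0.003) at 40 patients, and 4/10 vs 0/10 (p=0.087) at 20.

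**3. Undirected re-assessment change, no ultrasound effect.** Expected changes = N × flip rate.
- N=40: 40 × 0.05 = 2; 40 × 0.10 = 4; 40 × 0.20 = 8.
- N=20: 1, 2 and 4.

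Section 6 would count all of these as made by the ultrasound.

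**4. One-way drift, no ultrasound effect.** Suppose 60% are escalated before, 30% of those are dropped and 5% of the rest stepped up. Escalation after = 0.60 × 0.70 + 0.40 × 0.05 = 0.44. In 20,000 simulated studies of 40, the planned Fisher test was significant in 12% and exact McNemar in 52%.

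**5. Does the split remove drift?** Only in part.
- Under the drift in step 4, with equal prior escalation in both groups, downward change is 0.60 × 0.30 = 18% in each. The split comparison is significant in 2.7% of runs (N=40).
- With prior escalation of 30% (low) and 70% (not low), the same drift gives 0.30 × 0.30 = 9% vs 0.70 × 0.30 = 21% downward change, significant in 11% of runs with no ultrasound effect.
- Dividing by those escalated before restores equality: 9/30 = 30% and 21/70 = 30%. Direction of change must therefore be shown conditional on the starting recommendation.

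**6. Precision of the split.** Power of Fisher's test for downward change of 40% vs 10%: 49% (20 vs 20), 38% (28 vs 12), 15% (10 vs 10), 9% (14 vs 6).

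**The case against.** The case for leaving the plan alone has several parts.

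- *Changes are already counted.* This stands as far as it goes. A reader might infer that a null pooled comparison would conceal all the changes. It would not, because the planned frequency reports them. What is missing is direction and agreement with the scan.
- *The plan is descriptive and mostly temporal in wording.* Section 6.2 leaves hypothesis testing to a later proposal, and section 3.1 speaks only of evaluating potential. A reader might infer that the protocol claims every change as an ultrasound effect. That is too strong, since the causal wording on changed decisions is confined to one sentence in section 6. The sentence is nevertheless there, and sections 3.4.2 and 6.3.2 do plan tests.
- *The scan is the only new information the study supplies.* No second examination is planned, and the result, its interpretation and the second form are sent together (section 5.2.2). This makes ultrasound a likely cause of many changes. It does not exclude others, and the flip and drift rates above are assumptions.
- *Net escalation is a legitimate target.* The rationale runs mainly towards less escalation, and the secondary objective is a before/after comparison. This stands, and is why the pooled summaries should remain. Equal opposing flows are a constructed case.
- *The split is not a control.* This stands. A reader might see synovitis status as a free internal control that deserves to be the main Aim 2 contrast. The groups are not randomised, only drift common to both is netted out, and a patient not escalated before cannot move down. A best case such as 6 down and 0 up against 0 down and 5 up gives Fisher p=0.002, but it assumes that every change agrees with the scan.

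**Conclusion.** The point holds as a gap in reporting and attribution. The only test of recommendations is pooled, so opposite changes cancel in it; the illustration has 40% of recommendations changing with p=1.00. The change count is unaffected by cancellation, but it carries no direction and includes re-assessment change: 2 to 8 of 40, or 1 to 4 of 20, at assumed flip rates of 5% to 20%. With no re-assessment made without ultrasound, section 6's statement that "the number of patients for which the ultrasound information changed the decision-making of the clinical provider" will be tabulated goes further than the data can.

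The cancellation and the missing link to the scan follow from the documents. The sizes rest on assumed rates. The documents do not support reading this as a failed design, or the split as proof of an ultrasound effect. At 20 to 40 patients the split can show whether decisions tend to follow the scan, with wide intervals. This is a cheap improvement that the plan should adopt. The use of an unpaired test on paired answers is a separate matter.

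**What to change.** 1. In 3.4.2 and 6.3.2 (Aim 2), keep the pooled summaries and add descriptive pre-by-post tables of treatment recommendation and of disease activity rating, separately for low and not-low synovitis.
2. For recommendations, report in each group the proportion of pre-ultrasound escalations dropped and the proportion of non-escalations stepped up, with exact 95% intervals.
3. In section 6, replace the attribution with neutral wording, such as *change at re-assessment with ultrasound results available*.
4. State that the split is a concordance check, neither a control nor the main test: the groups are not randomised, it nets out only drift common to both, and the cells are small.

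Cost: plan wording and two further tables. No new data, visits or patients are needed. The downside is low precision per stratum; in the 20-patient illustration each conditional proportion rests on 5 patients.
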